3.7 Statistical analysing institute

The **institut** responsible for statistical analysis of the clinical trial is Beijing Key Tech Statistical Technology Co., Ltd., which is mainly responsible for:

- Statistical design of the plan;
- Randomization and blinding;
- Statistical analysis plan and statistical analysis report preparing;
- Statistical programming and statistical analysis;
- Preparation of analytical database to be reported;
- Review of statistics related documents such as clinical trial plan, CRF, data verification resolution, clinical research report, etc.

4. Background

4.1 Background of the disease

COVID-19 is a kind of pneumonitis caused by SARS-CoV-2. As a β -type coronavirus, single-stranded positive scene RNA virus, SARS-CoV-2 is enveloped, and particles are round or elliptic, often pleomorphic, with diameters of 60~140nm. The full genome length is about 29,800 basic groups. It involves 14 open coding frames that encodes 27 viral proteins [1]. People who are infected by SARS-CoV-2 are the major infection source and SARS-CoV-2 has the characteristic of human-to-human transmission. The infected person without symptoms also can be the infection source. Respiratory droplets and close contact are the main route of transmission. Aerosol transmission is also the possible way if the infected person is exposed to high-concentration aerosols for a long time in a relatively closed environment. SARS-CoV-2 can be separated from faeces and urine [2]. Fever, cough, dyspnoea and muscle pains are the most common symptoms of COVID-19. The incubation period of SARS-CoV-2 ranges from 1d to 14d, averaging at about 10d. SARS-CoV-2 is infectious during the incubation period, which is significantly different from SARS. Some study reported that 30%-60% of patients infected by SARS-CoV-2 have no symptoms or only mild symptoms, but they still have strong ability to spread the virus. These recessive infected persons might cause a new epidemic [3]. The basic reproduction number (R0) of SARS-CoV-2 ranges between 2.2 and 5.7 [4,5]. All people are susceptible to COVID-19 [6]. There's no specific medicine for COVID-19, but it can only be controlled according to the principle of early diagnosis, early quarantine and early ICU as much as possible. Basic therapy for pneumonia, antiviral drugs and anti-inflammatory combined with oxygen supply are applied as treatment of COVID-19. Suspected and diagnosed cases are quarantined at designated places. Critical cases are admitted to ICU as early as possible.

On March 11, 2020, WHO announced that COVID-19 epidemic has brought a "global epidemic". In China, COVID-19 is included into the List of Category B Infectious Diseases regulated by the *Law of the People's Republic of China on the Prevention and Treatment of Infectious Diseases*.

4.2 Research progresses of OVID-19 vaccine

Now, COVID-19 caused by SARS-CoV-2 has spreaded to more than 210 countries and regions. With the development of the COVID-19 epidemic, all countries in the world are devoted to research and development (R&D) of COVID-19 drugs and vaccines independently or cooperatively. At present, there are more than 120 candidate COVID-19 vaccines under development in the world. China is promoting vaccine R&D from five technical routes simultaneously, including inactivated vaccine, recombination genetic engineering vaccine, adenovirus vector vaccine, nucleic acid vaccine and attenuated influenza viral vector vaccine. Among them, the adenovirus vector vaccine achieved the quickest progress and it was the first COVID-19 vaccine which started the phase-II clinical study in the world.

The technical route for R&D of inactivated vaccine is the most mature, manifested by the explicit evaluation method and easy connection to scaled production process and easy transformation into multivalent vaccine. Since April, 2020, the National Medical Products Administration has approved clinical trials of COVID-19 inactivated vaccines which were developed by Wuhan Research Institute of Biological Products of China Biotechnology, Beijing Kexing Zhongwei Biotech Co., Ltd, Beijing Research Institute of Biological Products of China Biotechnology, and Institute of Medical Biology, Chinese Academy of Medical Sciences. Now, all of these vaccines have entered into the phase-III clinical tests. Emerging infectious diseases usually are characteristics of fast spreading, high lethality and lack of specific preventive and therapeutic drugs. Vaccine is the most economic and effective mean to control and prevent infectious diseases. With the spreading of COVID-19 epidemic, the importance of R&D of vaccine is further highlighted.

5. Preclinical Study of vaccines

5.1 Studies on animal immunogenicity

In the cynomolgus monkey animal model, one immunization of hindquarter muscle was performed to the cynomolgus monkey at 0d, 7d, 21d and 35d, respectively. The dosages were set 0.5ml per immunization for the 5 μ g dosage group (5 μ g/0.5ml), 0.5ml per immunization for the 10 μ g dosage group (10 μ g/0.5ml) and 2.0ml per immunization for the 40 μ g dosage group (40 μ g/0.5ml). Moreover, vein blood samples were collected from the hindquarters before the immunization and at 7d, 14d, 21d, 35d and 49d of the first immunization, from which serum was separated to detect the neutralizing antibody titer. According to test results, the cynomolgus monkey began to generate neutralizing antibodies since 7d after the immunization. The neutralizing antibody titer of serum increased gradually with the increase of immunization time and dosage, showing evident dose-effect relations. At 14d after the first immunization, the neutralizing antibody titer (GMT) of cynomolgus monkey serum in the 5 μ g, 10 μ g and 40 μ g dosage groups were 61, 67 and 197. At 21d after the first immunization, GMT of the 5 μ g and 10 μ g dosage groups declined slightly to 33 and 50, while the GMT of the 40 μ g dosage group increased to 279. After the booster immunization, GMT of the 5 μ g, 10 μ g and 40 μ g dosage groups increased significantly to 437, 394 and 1194 at 35d, and then to 1040, 905 and 1874 at 49d. To sum up, high level of neutralizing antibodies are generated at different time points after 2 weeks of immunization to the cynomolgus monkey by different dosages of COVID-19 inactivated vaccines. This proves the good immunogenicity of the COVID-19 inactivated vaccine to cynomolgus monkey.

In the rats animal model, one immunization of hindquarter muscle was performed to the rats at 0d, 7d, 21d and 35d, respectively. The dosages were set 0.5ml per immunization for the 5 μ g dosage group (5 μ g/0.5ml), 0.5ml per immunization for the 10 μ g dosage group (10 μ g/0.5ml) and 1.5ml per immunization for the 30 μ g dosage group (30 μ g/0.5ml). Moreover, vein blood samples were collected from the neck before the immunization and at 7d, 21d, 35d and 49d of the first immunization, from which serum was separated to test the neutralizing antibody titer. According to test results, the rats began to generate neutralizing antibodies since 7d after the immunization. The serum neutralizing antibody increased gradually with the increase of immunization time and dosage. GMT was 905~1114 at 21d, 2307~2941 at the 35d and 3620~5120 at 49d after the first immunization. From the first immunization to the 35d, there's no evident differences among three dosage groups in term of the average GMT. Moreover, GMT of the 5 μ g dosage group and the 30 μ g dosage group was higher than that of the 10 μ g dosage group at 49d. In a word, a high level of neutralizing antibodies is generated in rats after immunization with different dosages of COVID-19 inactivated vaccines. This proves the good immunogenicity of the COVID-19 inactivated vaccine to rats.

5.2 Studies on animal protective results

A total of 12 rhesuses were divided evenly into the high-dose group (n=4), low-dose group (n=4) and the model group (n=4) randomly. The dosages to the high-dose group and low-dose group were 10 μ g/0.5ml and 5 μ g/0.5ml. Each rhesus was injected with 0.5ml of the COVID-19 inactivated vaccine. The immunization schedule covered the 0d and 14d immunizations. Neutralizing antibodies were tested at 21d after the immunization and a challenge experiment was performed by the dosage of 10⁶TCID₅₀/pc at 22+2d after the immunization. During the experiment, ordinary symptoms of animals were observed and recorded every day. Throat swabs were collected at 3d, 5d and 7d after the a challenge experiment to test the viral loads.

According to test results, body temperature of the model group was not increased significantly. At 7d after the challenge experiment, the viral load of the throat swabs was $10^{5.83}$ copies/ml and the total mean of viral load was $10^{6.50}$ copies/ml, accompanied with moderate (1/4) ~severe (3/4) interstitial pneumonitis. The high-dose group didn't show abnormal body temperature and the viral load of throat swab at 7d after the challenge experiment was tested negative in comparison with the model group. The viral load of lung tissues decreased by 3.72lg and three rhesuses were detected negative. There were 4 cases of mild interstitial pneumonitis. The low-dose group didn't show abnormal body temperature and the viral load of throat swab at 7d after the challenge experiment was $10^{4.15}$ copies/ml in comparison with the model group, including 2 negative cases. Moreover, all cases were tested negative for viral load in lung tissues. There were 4 cases of mild interstitial pneumonitis. Results prove that high dose and low dose of COVID-19 inactivated vaccine (Vero cells) can protect the infected rhesuses significantly. A GMT higher than 1:32 can inhibit the SARS-CoV-2 effectively and relieve lesions of pneumonia.

5.3 Safety Assessment of animals

Muscle single-dose toxicity test of Rats Results showed that Sprague-Dawley was provided with single muscle injection of SARS-CoV-2 Vaccine (Vero cells), Inactivated at 4 doses/pc (40µg/pc), showing no deaths or moribundity. Hence, the maximum tolerance dose (MTD) is higher than or equal to 40µg/pc.

Muscle repeat-dose toxicity test of rats

Results showed that all dose groups presented transient growths of Neut and FIB and a reduction of Lymph after repeat muscle injections of COVID-19 inactivated vaccine (Vero cells) to rats every week or every 2 weeks at the doses of 5, 10 or 30 µg/pc for 7 weeks, totally 5 injections. At the end of immunization, Glb and AST increased, while Alb and A/G decreased. All these four parameters recover to the normal levels at the end of recovery period. Irritant and inflammatory reactions which might be related with aluminum adjuvant could be seen on outer membrane of ischiadic nerve and skins (surrounding the mammary gland) of local injection group and the 30 µg/pc group, while no evident systematic toxic reactions were observed. Certain levels of anti-S proteins IgG antibodies and neutralizing antibodies can be detected from animals, but no immunotoxicity reactions have been seen. According to current data, the No Observed Adverse Effect Level (NOAEL) was 30 µg/pc.

Muscle repeat-dose toxicity test of cynomolgus monkey

According to test results, irritant reactions (mild or moderate granulomatous inflammation) related with test samples can be seen after local injection of SARS-CoV-2 Vaccine (Vero cells), Inactivated every week or every 2 weeks for 7 successive weeks (total 5 injections) under the dosage of 5, 10 and 40 µg/pc. No systematic toxic reactions were observed. Certain levels of anti-S proteins IgG antibodies and neutralizing antibodies can be detected from animals, but no immunotoxicity reactions have been seen. Therefore, the NOAEL was 40 µg/pc.

According to the systematic positive allergic reaction test results of guinea pigs, three successive sensitizations after muscle injection of SARS-CoV-2 Vaccine (Vero cells), Inactivated every two days at the dosages of 0.1 dose/pc and 1 dose/pc will cause allergies. Intravenous injections at the dosages of 0.2 dose/pc and 2 doses/pc were performed at 14d and 21d of the last sensitization, but the guinea pigs didn't show any systematic positive allergic reaction.

6. Product features

SARS-CoV-2 Vaccine (Vero cells), Inactivated is manufactured by inoculating novel coronavirus onto Vero cells and through viral culture, harvest, inactivation, purification and adjuvant adsorption. It is used to prevent COVID-19. SARS-CoV-2 Vaccine (Vero cells), Inactivated is a uniform milky white suspension after shaking, without clot or foreign matters. It contains SARS-CoV-2 (inactivated) antigens, Al(OH)₃, NaCl, phosphate and sterile water for injection.

7. Purpose of study

To evaluate the safety and immunogenicity of the SARS-CoV-2 Vaccine (Vero cells), Inactivated in healthy adults aged 18 and above

8. Study design

8.1 Design method

This study is a randomized, double-blind, placebo-controlled clinical trial (phase II)

8.2. Sample size

Following the requirements of “Technical Guidelines for Clinical Trials of Vaccines”, there're altogether 1000 subjects taking part in this phase II clinical trial, among which 750 are from the 18-59-year-old group (including 250 in the 0-28-56 d immunization group, 250 in the 0-28 d group, and 250 in the 0-14 d group.) Another 250 subjects are 60 years old and above who take part in the 0-28-56 d immunization group. Sample distribution is shown in Table 1.

Table 1. Grouping and sample distribution of phase II trial

Group	Dosage groups	Number of cases	Vaccine No.	Immunization No.	Immunization schedule		
					First immunization	Second immunization	Third immunization
Aged 18-59 3-dose group	middle-dosage group	100	A2001~ A2250	3	0d	28d	56d
	High-dose group	100		3	0d	28d	56d
	Placebo group	50		3	0d	28d	56d
Aged 18-59 2-dose 0-28d group	middle-dosage group	100	A2251~ A2500	2	0d	28d	—
	High-dose group	100		2	0d	28d	—
	Placebo group	50		2	0d	28d	—
Aged 18-59 2-dose 0-14d group	middle-dosage group	100	A2501~ A2750	2	0d	14d	—
	High-dose group	100		2	0d	14d	—
	Placebo group	50		2	0d	14d	—
Aged ≥60 group	middle-dosage group	100	B2001~ B2250	3	0d	28d	56d
	High-dose group	100		3	0d	28d	56d
	Placebo group	50		3	0d	28d	56d
Total		1000					

8.3 Random and blind tests

The clinical study used the test design of random, double-blind, placebo control groups. Randomized statisticians generated random blind bases by using the SAS 9.4 or higher version of software. In each of the immunization groups (no matter from 18-59-year-old group or ≥60-year-old group), the subjects are allocated into medium-dose group, high-dose group and placebo group at a ratio of 2:2:1. After qualified respondents were screened, they were allocated and numbered according to the recruitment order. These respondents were injected with corresponding number of vaccines for study. Experimental vaccine and placebo had the same package and double blinks for the clinical test were realized according to the blind setting method of vaccines.

Randomized statisticians generated standby blind bases of vaccine by using the SAS 9.4 or higher version of software, and prepare backup vaccines according to the proportions of middle dose, high dose and placebo of 2:2:1. When colors of experimental vaccines are changed or some damages are observed, the vaccination staffs shall report the supervisor and principal investigator to initiate the backup vaccine use program, in which the backup vaccine No. is acquired by the online backup vaccine acquisition system and the backup vaccine is used to replace the research vaccine.

8.4 Vaccine No.

In the clinical test, the applier was responsible for providing qualified experimental vaccines and placebo

and it could authorize the non-blind randomized statisticians to organize vaccine numbering. According to random blind bases, experimental vaccines and placebo were encoded into serial numbers randomly (vaccine per person has the sole serial No.). Moreover, the sole serial No. and other relevant contents shall be marked uniformly on the external package.

Blind bases are kept secretly by two people in duplicates and the coding materials shall be sealed. Blind coding staffs are prohibited to participate in clinical tests and disclose the blind coding contents to people who participate in clinical tests.

Backup vaccine: 100 backup vaccines, including 40 middle-dose vaccines, 8 high-dose vaccines and 20 placebos, were provided except experimental vaccines for injection to the planned respondents. Vaccines which cannot be used shall be replaced by backup vaccines. In the clinical test, when backup vaccine has to be used, the vaccination staffs opened the envelope which agrees with the research No. of the respondents and then injected the backup vaccine to the respondents according to the recorded No. in the envelope.

8.5 Unblinding and emergency unblinding

In this trial, representatives of the sponsors, investigators, and statisticians will unblind the study cohorts together after blinded review of the data at the end of 28 d safety observation and immunogenicity data analysis when the last subjects in different cohorts receive the final dose.

The randomization statistician will prepare contingency letters while blinding, each letter containing a random password for unblinding use. Each random password corresponds to any study number, and the true group of that study number is fed back through the online unblinding system. Each random password represents one chance to unblind only one study number. A random password will expire when used, it is invalid for the unblinded study number. In this study, 10 emergency envelopes are prepared for the phase II clinical trial, which are kept by the person in charge on site. The emergency envelope opening will be checked in the blinded audit.

In case of an emergency (such as a serious adverse event) in the field operation, the investigator may perform an individual emergency unblinding if he or she deems it necessary to clarify information about the experimental vaccine administered to the subject so that appropriate treatment measures can be taken. The person in charge of the site will open and read the emergency letter, log in to the online emergency unblinding system with the unblinding random password inside the letter, and perform emergency unblinding in accordance with the instructions. The investigator involved in the unblinding should sign the name with date and time, and given the reason for unblinding. Investigators should evaluate the relationship between adverse events and the experimental vaccine prior to emergency unblinding. Investigators should immediately notify the sponsor via a 24-hour emergency telephone before conducting emergency unblinding for any reason during the study period. The reason for emergency unblinding must be recorded in the subject's CRF. Subjects unblinded will withdraw from the study, and their safety data will be included in the safety set and possible FAS.

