8.7.2 Secondary endpoints

- Incidence of adverse events within 28 d after each dose of vaccine.

- Incidence of serious adverse events from the first dose to 12 months after full-course immunization.
- The antibody level of IgG antibody (ELISA method) against COVID-19 virus 28 days after the whole immunization
- Positive seroconversion rate and antibody level of neutralizing antibody and IgG antibody (ELISA method) against COVID-19 virus 28 days after the 2nd dose (as for 3-dose immunization group) or 14 days after the whole immunization (as for 2-dose immunization group)
- Positive seroconversion rates and the levels of novel coronavirus neutralizing antibodies and IgG antibodies (ELISA method) at 3, 6 and 12 months after full-course immunization.

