9.4 Exclusion Criteria for Subsequent Vaccinations

After the enrollment, during the study period, if the COVID-19 epidemiological history, suspected COVID-19 clinical manifestations appear, epidemiological investigation and nucleic acid tests shall be carried out immediately, chest CT shall be taken if necessary, and the subjects shall undergo quarantine observation according to local epidemic prevention and control. If the subject is diagnosed with a COVID-19, he/she shall withdraw from the clinical trial, and accept the reasonable treatment from local center for disease control as required.

If one of the following (1) to (3) adverse events (AE) occurs, the vaccination shall be prohibited, other research procedures can be continued according to researchers' discretion; If one of the following (4) to (5) adverse events occurs, it is up to the investigator to determine whether the vaccination shall be continued; If one of the following (6) to (7) adverse events occurs, the vaccination shall be delayed within the time window specified in the protocol.

- (1) Any serious adverse events with cause association with vaccination;
- (2) Serious allergic response or hypersensitivity after the vaccination (including urticaria/rash within 30 minutes after vaccination);
- (3) Any diagnosed or suspected auto-immune diseases or immunodeficiency diseases (including human immunodeficiency virus (HIV) infection).
- (4) Emerging chronic diseases after vaccination or acute attack of chronic diseases;
- (5) Severe intolerable adverse reaction occurs.
- (6) Suffering from acute diseases at vaccination (acute diseases refer to moderate or severe diseases with or without fever);
- (7) Axillary temperature ≥ 37.0 °C at vaccination.

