10.4.8 Medical management of adverse events

Subjects should be informed to record clinically significant adverse events at any time. Early suspected symptoms of COVID-19 (such as fever, dry cough, fatigue, nasal congestion, rhinorrhoea, pharyngalgia, myalgia, diarrhea, polypnea, and dyspnea), COVID-19 infection, grade 3 or above AEs and SAEs, if any, should be reported, at all times, to the investigator who should conduct investigation, verification and follow-up after being informed, until such events are resolved, and finally complete the detailed case investigation and follow-up records. In case of severe or fatal COVID-19 infection, further thematic investigations are required to determine the presence of ADE/VED. If subjects experience grade 3 or above AEs or SAEs after vaccination, the investigator should provide them with appropriate treatment or medical consultation in a timely manner to alleviate or relieve their suffering. If necessary, the green channel for medical treatment should be initiated to ensure timely medical treatment, and the medical measures and results should be recorded in detail during this process.

Adult female subjects are required to take effective contraceptive measures within 2 weeks before enrollment and 1 month after full-course vaccination. If an unplanned pregnancy occurs in subjects between enrollment and 1 month after full-course vaccination, the investigator should immediately stop vaccination, prematurely terminate all studies, and record it as an AE. The investigator should follow up the health of both subjects and children up to 12 months after birth.

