10.8 Initial analysis and additional analysis

Initial analysis: After the last subject completes the visit and immunogenicity test on Day 28 after the last immunization, all parties jointly complete the data review and database locking before unblinding for statistical analysis.

Updated analysis: Long-term safety observation and statistical analysis of immune persistence will be performed after completion of SAE observation at 12 months after full-course immunization and completion of antibody detection for immune persistence observation at 3, 6 and 12 months after full-course immunization.

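### Investigator representatives learn the treatment codes before the 12-month SAE endpoint is complete, and two withdrawal rules may leave later SAEs uncollected

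*Protocol*

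**What the plan says.** **Planned unblinding.** Section 8.5 states that "representatives of the sponsors, investigators, and statisticians will unblind the study cohorts together after blinded review of the data". This happens after the 28-day safety observation and immunogenicity data of the last subjects to receive a final dose. Section 10.8 adds that "all parties jointly complete the data review and database locking before unblinding for statistical analysis". Neither section gives a time to lock.

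**The endpoint that continues.** Section 8.7.2 lists as a secondary endpoint: "Incidence of serious adverse events from the first dose to 12 months after full-course immunization". Sections 8.8.2 and 10.4.2 collect SAEs at visits or calls at 3, 6, 9 and 12 months, and through subjects' own reports, which the researchers investigate and verify. Relatedness is judged on a five-level scale (10.4.6). Section 8.10 uses it: one possibly related grade 4 event or SAE suspends the trial, and one possibly related death ends it.

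**Emergency unblinding.** Section 8.5: "In this study, 10 emergency envelopes are prepared for the phase II clinical trial", and each opens one study number. The investigator must assess causality before the code is broken. Then: "Subjects unblinded will withdraw from the study, and their safety data will be included in the safety set and possible FAS". Section 9.5, item 4, lists emergency unblinding among the grounds for exclusion by the investigator.

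**COVID-19.** Section 9.4: "If the subject is diagnosed with a COVID-19, he/she shall withdraw from the clinical trial". Section 10.4.8 requires COVID-19 infections, grade 3 or higher AEs and SAEs to be followed until resolved. For severe or fatal infection it says "further thematic investigations are required to determine the presence of ADE/VED".

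**The concern.** The trial is described as double-blind (8.1, 8.3), yet from the initial analysis onward the protocol keeps no one who collects or judges SAEs blind. Knowing the arm can influence which events are pursued and reported, and how a possibly related event is classed. That classification feeds a safety comparison between arms and also the suspension and termination criteria, which apply throughout the study.

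The withdrawal rules raise a separate problem. A code break will often follow a serious event, and a COVID-19 diagnosis is itself an outcome of interest. Ending study participation at that point makes the end of follow-up depend on what happened to the subject. The endpoint in 8.7.2 runs to 12 months for everyone, with no exception for these subjects. The wording on the FAS adds a smaller ambiguity, because it does not say what decides whether an unblinded subject belongs to that set.

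**Working it through.** **A. How much of the SAE window follows unblinding?** The protocol gives no figure for this, so there is none to reproduce.

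Inputs:
- Last-dose day D = 14, 28 or 56 (Table 1).
- SAE window: first dose to 12 months after the last dose, taken as D + 365 days (8.7.2).
- Earliest unblinding for the last-enrolled subject of a cohort: day D + 28 (8.5).
- Accrual: about 16 − 15 = 1 month (8.9), so a = 30 days of extra blinding for the first-enrolled subject and a = 0 for the last. This is an inference.
- L = days from the last subject's day 28 to unblinding (testing, review, lock). This is not stated, so 0 to 120 days is an assumption.

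Share after unblinding = 1 − (D + 28 + a + L)/(D + 365) = (337 − a − L)/(D + 365).

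With each cohort unblinded separately (ranges run from first- to last-enrolled subject):

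| Schedule | Window (days) | L = 0, a = 0 | L = 60 | L = 90 | L = 120 |
|---|---|---|---|---|---|
| 0-14 d | 379 | 337/379 = 88.9% | 247/379 to 277/379 = 65–73% | 57–65% | 49–57% |
| 0-28 d | 393 | 337/393 = 85.8% | 247/393 to 277/393 = 63–70% | 55–63% | 48–55% |
| 0-28-56 d | 421 | 337/421 = 80.0% | 247/421 to 277/421 = 59–66% | 52–59% | 44–52% |

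Break-even: the first-enrolled 3-dose subject is at 50% when 337 − 30 − L = 210.5, so L = 96.5 days. A mid-accrual 3-dose subject (a = 15) is at 50% when L = 111.5 days. Below about 96 days to lock, more than half of every subject's window is after unblinding.

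Sensitivity: if all cohorts are unblinded together after the last 3-dose subject (assuming they enrol over the same month), the 0-14 d share is (379 − 84 − a − L)/379. That gives 70–78% at L = 0, 54–62% at L = 60, 46–54% at L = 90, and 145/379 to 175/379 = 38–46% at L = 120.

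**B. What happens after withdrawal?**
- 8.7.2 requires SAE incidence to 12 months.
- 8.5 and 9.5, item 4, take the emergency-unblinded subject out of the study. The maximum is 10/1000 = 1.0% of subjects.
- 9.4 takes the COVID-19-diagnosed subject out of the trial. No number can be given.
- 9.5 follows AE/SAE withdrawals until the event resolves, a sentence that stands under voluntary withdrawal. 10.4.8 follows COVID-19, grade 3 or higher AEs and SAEs until resolved.
- No section says that SAE collection continues to month 12 after either withdrawal. Where longer follow-up was intended, the protocol says so: 10.4.8 ends all studies for a pregnant subject but follows mother and child to 12 months after birth.

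The triggering event is therefore kept and followed, while a later, separate SAE in the same subject has no stated route into the data.

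**C. FAS.** Section 10.7.3.2 defines the FAS by randomisation, at least one dose, a pre-immunisation sample and valid antibody values. Unblinding is not an exclusion there, so the wording in 8.5 is looser than the definition it refers to.

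**The case against.** Staged unblinding is openly pre-specified, with an initial and an updated analysis (10.8). The primary endpoints are antibody measures at day 28, taken before unblinding. The affected endpoint is secondary, and SAEs rest on fairly concrete outcomes such as death, hospitalisation and disability (10.4.1). These points stand and limit the weight of the finding. They do not cover relatedness, which is a judgement.

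A reader might infer more than the text supports:
- *Every subject's follow-up is unblinded from day 28.* No. It is after the last subject's day 28 plus testing, review and lock, so 80–89% is an upper bound.
- *The follow-up is open-label and placebo recipients will seek another vaccine.* Section 8.5 names only representatives of three parties. Nothing says that subjects are told their group, nor that the representatives present are the staff who assess SAEs. The gap is that nothing keeps those staff blind.
- *The trial loses the subjects most likely to have events.* The triggering SAE has already occurred, its causality is judged first, and it stays in the safety set. For overall SAE incidence the subject already counts as a case. What can be lost is later SAEs: these affect event counts, related-SAE incidence if the first event was judged unrelated, and incidence in COVID-19 subjects whose infection was not serious.
- *The FAS drops subjects by outcome.* The natural reading is FAS membership if the 10.7.3.2 criteria are met.
- *Withdrawal defeats the ADE/VED inquiry.* That inquiry concerns the index infection, which 10.4.8 does follow.

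**Conclusion.** The point holds in a limited form. Investigator representatives receive the allocation well before the 12-month SAE endpoint is complete, and the protocol preserves no blinded assessor. At most 80–89% of a subject's SAE window follows unblinding. The share is about 44–73% with cohort-wise unblinding, 60 to 120 days to lock (assumed) and one month of accrual (inferred), and lower for the 0-14 d cohort if all cohorts are unblinded together.

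Separately, Sections 8.5, 9.4, 9.5 and 10.4.8 do not together deliver the 12-month SAE collection that 8.7.2 requires for emergency-unblinded subjects (at most 1.0%) and COVID-19-diagnosed subjects (number unknown). The triggering event itself is not lost.

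The direction and size of any bias cannot be computed, because the protocol gives no SAE rate. The statistical analysis plan is not at hand, but who learns the codes and who stays in follow-up are rules the protocol itself sets. This is a worthwhile, inexpensive improvement to a secondary safety endpoint and does not threaten the primary analysis.

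**What to change.** 1. **Section 8.5 and 10.8.** At the initial analysis, release individual codes only to the reporting statisticians and a named sponsor/report team. Keep site staff who collect SAEs or judge causality, the subjects and the laboratories blinded until the 12-month lock. State whether cohorts are unblinded separately or together.
2. **Sections 8.5, 9.4, 9.5 and 10.4.8 against 8.7.2.** Reconcile them so that emergency-unblinded and COVID-19-diagnosed subjects who consent remain in the scheduled SAE follow-up to 12 months. This concerns data collection only; no vaccination rule is proposed. Handling of antibody titres after infection can be left to the statistical analysis plan.
3. **FAS wording in 8.5.** Say that the subject is included in the FAS if the criteria of 10.7.3.2 are met.

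Cost: protocol wording and an access-control document. No visits are added, since the 3-, 6-, 9- and 12-month contacts already exist (8.8.2). The real burden is organisational. The body that runs the trial also writes the summary report (3.1), so any report author there who also assesses SAEs must either hand over one of those roles or wait, with the site staff, until 12 months for individual codes. Emergency unblinding for a subject's care remains available throughout.
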